#### 4.9.3 Sexual Satisfaction and Lubrication

Sexual Satisfaction and Lubrication will be assessed with the following questions, asked at baseline and at each subsequent visit:

- Baseline: What impact did your most recent contraceptive method have on your sex life in the last 4 weeks of use?
- Visit 3-5: What impact has the study contraceptive method had on your sex life since your last study visit?

The response set for these questions is as follows:

- a. My sex life was a lot better than before
- b. My sex life was a little better than before
- c. My sex life was no different than before
- d. My sex life was a little worse than before
- e. My sex life was a lot worse than before

The Female Sexual Function Index (FSFI), a 19-item questionnaire, provides scores on six domains of sexual function (desire, arousal, lubrication, orgasm, satisfaction, and pain) as well as a total score. Only question 10 from the FSFI will be summarized according to the following response set:

- 10. Over the past 4 weeks, how difficult was it to maintain your lubrication ("wetness") until completion of sexual activity or intercourse?
  - u. No sexual activity
  - f. Extremely difficult or impossible
  - g. Very difficult
  - h. Difficult
  - i. Slightly difficult
  - j. Not difficult

All variables given above will be summarized using frequency and percentage by visit and outcome categories. Unscheduled visits will be grouped with the associated visit (e.g., visit 3.1 will be included with visit 3).

#### **4.10 Missing Data Handling**

##### **4.10.1 Imputing partial AE and prior/concomitant medication start dates**

- a) If the year is unknown, the date will not be imputed if the stop date of the event is earlier than the first dose time; otherwise, it will be imputed as the year of the first dose time.
- b) If the month is unknown, then:
  11. If the year matches the first dose date, then impute to the month and day of the first dose date.
  12. Otherwise, assign 'January'.
- c) If the day is unknown, then:
  13. If the month and year match the first dose date, then impute to the day of the first dose date.
  14. Otherwise, assign '01'.

#### 4.10.2 Imputing partial AE and prior/concomitant medication stop dates

- a) If the year is unknown, the date will not be imputed if the start time of the event is after the last dose time, otherwise it will be imputed as the year of the last dose time.
- b) If the month is unknown, then assign 'December'.
- c) If the day is unknown, then impute to the last day of the month.

#### 4.11 Pregnancy Intendedness

The pregnancy intendedness scale and its change from the baseline will be summarized descriptively by visit. Unscheduled visits will be grouped with the associated visit (e.g., visit 3.1 will be included with visit 3).

##### 4.11.1 Determination of Sample Size

Simulation methods are used to evaluate the likelihood of various sample sizes providing enough information to test the primary hypothesis (one-sided Type 1 error of 0.025) and enough use cycles of Amphora gel to address other regulatory requirements. The six month (183 d) cumulative pregnancy percentage was estimated using Kaplan-Meier methods.

The sample size determination assumes the following:

- Study drug pregnancy percentage: 16.5%
- 26.5% of subjects fail to qualify for the primary efficacy analysis population
- Of the subjects that qualify for the primary efficacy analysis population, the average number of evaluable efficacy cycles per subject: 3.17
- Exponential hazard for:
  - Pregnancy rate first 6 months: 16.5%
  - Drop out month 1: 10%
  - Drop out months 2-6: 38%

With 1349 participants aged 18 through 35 years (inclusive), the study will have 90% power to ensure that the upper limit of the 95% CI of the cumulative seven-cycle pregnancy rate is less than or equal to 21%. The expected number of completers is 515 and the expected number of cycles evaluable for safety is at least 3143.

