9.2 Sample Size

The sample size determination assumes the following:

- Study drug pregnancy percentage: 16.5%
- 26.5% of subjects fail to qualify for the primary efficacy analysis population
- Of the subjects that qualify for the primary efficacy analysis population, the average number of evaluable efficacy cycles per subject: 3.17
- Exponential hazard for:
 - Pregnancy rate first 6 months: 16.5%
 - \circ Drop out month 1: 10%
 - Drop out months 2-6: 38%

With 1349 participants aged 18 through 35 years (inclusive), the study will have 90% power to ensure that the upper limit of the 95% CI of the cumulative seven-cycle pregnancy rate is less than or equal to 21%. The expected number of completers is 515 and the expected number of cycles evaluable for safety is at least 3143.

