9.8.3 Sensitivity Analyses

Sensitivity Analysis with Respect to the Cycle Range: The primary analysis will be repeated with the cycle length expanded from 21-35 days to 21-42 days.

Sensitivity Analysis of the Dosing Time with Respect to Sexual Intercourse: To evaluate the effect of the dosing time with respect to sexual intercourse, subgroup analyses for the primary analysis will be performed by the dosing time category performed according to the following

dosing time categories with respect to sexual intercourse: < 1 hour, < 1.5 hour, < 2 hours, <2.5 hours, and all cycles (without respect to dosing time).

Sensitivity Analysis with Respect to Completers and Non-completers: To evaluate differences between completers and non-completers the primary analysis will be repeated for just completers. A completer is defined as a woman who becomes pregnant within 7-cycles (inclusive) or who completes the 7 cycles with no pregnancy.

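### The 90% power for the seven-cycle rate comes from a six-month (183-day) model and does not follow from the plan's own 3.17 evaluable cycles per woman, which allow at most about 76% at a true rate of 16.5%

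*SAP*

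**What the plan says.** SAP 4.11.1 (Determination of Sample Size) says that sample sizes were evaluated by simulation at a one-sided type I error of 0.025, and that "The six month (183 d) cumulative pregnancy percentage was estimated using Kaplan-Meier methods". The pregnancy hazard is exponential, with "Pregnancy rate first 6 months: 16.5"%. A separate line, without a period, reads "Study drug pregnancy percentage: 16.5"%. Dropout is 10% in month 1, then "Drop out months 2-6: 38"%. The plan expects 26.5% of enrolled women not to qualify for the primary efficacy population. For those who qualify, it lists "the average number of evaluable efficacy cycles per subject: 3.17".

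From these inputs, with 1349 women, the SAP claims 90% power that the "upper limit of the 95% CI of the cumulative seven-cycle pregnancy rate is less than or equal to 21"%. It adds: "The expected number of completers is 515 and the expected number of cycles evaluable for safety is at least 3143". Protocol 9.2 repeats the inputs and the claim, but not the sentence about 183 days.

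The primary endpoint (SAP 4.7.2) is the seven-cycle Kaplan-Meier percentage in the MITT population, with a 95% interval based on Greenwood's method. Under SAP 4.7.2.1 only evaluable cycles count, normally 21 to 35 days long, and they are compressed into a contiguous sequence for each woman.

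**The concern.** Two features of the power statement do not fit the analysis it is meant to support.

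- **Period.** The quantity simulated is a percentage at 183 days; the quantity tested is a percentage after seven cycles. Seven evaluable cycles can span 147 to 245 days. If 16.5% is reached at 183 days and seven cycles last longer, the true seven-cycle rate is above 16.5% and the gap to 21% is below 4.5 points. If they are shorter, the gap is wider.
- **Exposure.** The precision of the Kaplan-Meier estimate depends on how many cycles enter it. The plan lists 3.17 per woman for the primary efficacy population, but its dropout rates imply clearly more. Power should reflect the smaller figure.

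At stake is whether the trial has the stated chance of meeting its only primary criterion.

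**Working it through.** **Inputs** (SAP 4.11.1, Protocol 9.2): N = 1349; 26.5% not qualifying; 16.5%; dropout 10% then 38%; 3.17 evaluable cycles; limit 21%; z = 1.96.

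**Step 1. The printed counts.**
- Qualifying women: 1349 × 0.735 = 991.5.
- Completers: 991.5 × (1 − 0.10 − 0.38) = 991.5 × 0.52 = 515.6, which matches 515. Reading 38% as a share of those remaining gives 991.5 × 0.90 × 0.62 = 553, which does not.
- Cycles: 991.5 × 3.17 = 3143, as printed.

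The 515 is retention at month 6. Protocol 9.8.3, however, says: "A completer is defined as a woman who becomes pregnant within 7-cycles (inclusive) or who completes the 7 cycles with no pregnancy". This suggests that month 6 was treated as the end of cycle 7.

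**Step 2. Reproducing the 90%.** Daily hazard h = −ln(0.835)/183 = 0.000985. With the additive dropout reading and plain Greenwood variance at 183 days, SE = 0.0141.

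Power = Φ((0.21 − 0.165)/0.0141 − 1.96) = 89.3%.

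The conditional dropout reading gives 90.3%. Simulation (4000 runs) gives 87.5% and 89.3% respectively. The 3.17 was not used. As a check on the method, the superseded N of 1157 in the Revision History gives 84% to 85% by the same route, against the 85% recorded there.

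Equating month 6 with the end of cycle 7, these dropout inputs give 5.05 cycles started and 4.48 completed per woman, against the listed 3.17.

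**Step 3. From 183 days to seven cycles.** 183/7 = 26.1 days. Holding h constant, the seven-cycle rate is 1 − exp(−7ch) for a mean cycle of c days. The mean cycle length is my assumption; the only nominal length in the documents is 28 days, in the Pearl comparison of SAP 4.7.3.4. The table uses the dropout inputs only (additive reading).

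| Mean cycle (days) | Seven-cycle rate | SE | Power, plain interval | Power, log-log interval |
|---|---|---|---|---|
| 25 | 15.8% | 0.0137 | 96% | 91% |
| 26 | 16.4% | 0.0140 | 90% | 83% |
| 27 | 17.0% | 0.0143 | 80% | 72% |
| 28 | 17.6% | 0.0146 | 65% | 58% |
| 29 | 18.1% | 0.0149 | 49% | 44% |
| 30 | 18.7% | 0.0152 | 33% | 30% |

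If the hazard halves after day 183, plain-interval power is 85%, 79% and 72% at 27, 28 and 29 days. If 16.5% is instead the seven-cycle rate, the dropout inputs give 88% to 90% over 25 to 30 days (80% to 82% log-log).

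**Step 4. Using the 3.17 cycles.** Take 16.5% as the seven-cycle rate. A constant hazard gives a per-cycle probability q = 1 − 0.835^(1/7) = 0.0254. With n_j women at risk in cycle j,

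SE = 0.835 × √( Σ q / (n_j(1 − q)) ), with Σ n_j = 3143.

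For a fixed total, Σ 1/n_j is smallest when all n_j are equal, so the even spread gives the highest power.

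| Women at risk | SE | Power at 16.5% | Seven-cycle rate that gives 90% |
|---|---|---|---|
| Even: 449 in every cycle | 0.0168 | 76% | 15.6% |
| 991.5 in cycle 1, then 358.6 per cycle | 0.0180 | 71% | 15.3% |
| Geometric, ratio 0.7145 | 0.0209 | 58% | 14.5% |

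For the even case: Φ(0.045/0.01684 − 1.96) = Φ(0.712) = 76%. Simulation with the plain interval gives 74%, 69% and 58% for the three rows. The even spread is generous, because compression moves each woman's first evaluable cycle into position 1, so most of the 991 should be at risk there.

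Combining 3.17 cycles with the six-month reading gives about 71% to 87% at a 25-day cycle and 36% to 51% at 28 days, from geometric to even attrition.

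**The case against.** The case for the plan has four parts.

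- **The 16.5% may already be a seven-cycle rate.** One of the two 16.5% lines carries no period. On that reading the first problem reduces to wrong labels. This stands as a possibility, but it leaves Step 4 untouched.
- **The 3.17 may have been meant only for the use-cycle count.** SAP 4.11.1 says that the simulation also had to provide enough use cycles for other regulatory requirements, and it describes the 3143 as a minimum of cycles evaluable for safety. However, the 3.17 is itself labelled as efficacy cycles for women in the primary efficacy population, and those are the cycles the primary analysis uses. Intent is uncertain, but the power does not follow from the list as printed.
- **The 76% ceiling assumes a constant hazard.** This is correct. If the per-cycle hazard falls by 30%, 40% or 50% each cycle, with 16.5% held at seven cycles, power under geometric attrition rises to 77%, 84% and 89%. These are steep falls, none reaches 90%, and the plan's own assumption is an exponential hazard.
- **The simulation program is not in the documents.** The model is inferred, and no single simulated reading matches both 515 and 90% exactly: the additive reading fits 515 but simulates at 87.5%, and the conditional reading simulates at 89.3% but gives 553. This limits certainty about what was run. It does not help the claim, because neither reading used the 3.17. Other attempts also fall short: a one-sided 0.05 level gives 85%, and applying 3.17 to all 1349 women gives 87.6% at best.

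**Conclusion.** The concern holds. The stated 90% is the power of a 183-day model driven by the dropout rates, not of the seven-cycle analysis over evaluable cycles that the plan specifies.

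- If 16.5% is a six-month rate, power depends on a mean cycle length that the plan does not give. It is below 90% for any mean above about 26 days even before the 3.17 is applied.
- If 16.5% is the seven-cycle rate, the listed 3.17 cycles support 58% to 76%. Reaching 90% would need a true seven-cycle rate of 14.5% to 15.6%.

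These figures rest on my assumptions about mean cycle length, hazard after day 183, attrition pattern and interval scale. SAP 4.7.2 names Greenwood's method but not the scale, and a log-log interval lowers power further. Only the statement of power is affected; the 21% rule, the type I error and the primary analysis are not. The point should be fixed.

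**What to change.** 1. In Protocol 9.2 and SAP 4.11.1, state which period the 16.5% covers, the assumed mean cycle length and the confidence interval scale. If 16.5% was meant as the seven-cycle rate, correct the six-month and 183-day labels.
2. Rerun the simulation with the seven-cycle Kaplan-Meier percentage over compressed evaluable cycles as the estimand, using an attrition pattern that averages 3.17 evaluable cycles per qualifying woman. If 3.17 was not meant to describe primary-analysis exposure, say so and give the figure that does.
3. Restate the expected seven-cycle rate and the power in both sections, leaving N unchanged.

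The cost is one simulation rerun and wording in two sections. N, the endpoint and the primary analysis stay as they are. The restated power will probably be lower.

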### 4.7.2 Primary Efficacy Analysis

The primary efficacy endpoint is the cumulative percentage of typical-use 7-cycle pregnancy. The primary hypothesis to be tested is whether subjects using Amphora vaginal gel have a 7-cycle cumulative pregnancy percentage less than or equal to 21%, that is,

$$H_0: \pi_A > 21\% \text{ vs. } H_A: \pi_A \leq 21\%$$

where  $\pi_A$  represents the 7-cycle cumulative pregnancy percentage for Amphora. The Kaplan-Meier (KM) estimate and its 95% CI (based on Greenwood's method) of the 7-cycle cumulative pregnancy percentage of women in the MITT population will be calculated. If the upper bound of the 95% CI is  $\leq 21\%$ , then the null hypothesis will be rejected and the conclusion will be that the 7-cycle cumulative pregnancy percentage is  $\leq 21\%$ .

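### Power of 90% is stated for the seven-cycle rate, but the 16.5% behind it is set at six months (183 days), and neither document links the two time points

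*SAP*

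**What the plan says.** The primary test concerns seven menstrual cycles. SAP 4.7.2 asks "whether subjects using Amphora vaginal gel have a 7-cycle cumulative pregnancy percentage less than or equal to 21" per cent. It decides by the upper bound of the Kaplan-Meier "estimate and its 95% CI (based on Greenwood's method) of the 7-cycle cumulative pregnancy percentage of women in the MITT population".

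The sample-size section, SAP 4.11.1, uses a "one-sided Type 1 error of 0.025" and says of its simulation: "The six month (183 d) cumulative pregnancy percentage was estimated using Kaplan-Meier methods". Among the exponential hazards, both SAP 4.11.1 and Protocol 9.2 list "Pregnancy rate first 6 months: 16.5" per cent. Both also carry a separate line with no time point, "Study drug pregnancy percentage: 16.5" per cent. The conclusion reads "With 1349 participants aged 18 through 35 years (inclusive), the study will have 90% power", and the quantity it refers to is the seven-cycle rate against 21%. Protocol 9.2 makes the same power statement but does not contain the 183-day sentence.

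On cycle length, both documents accept cycles of 21 to 35 days as evaluable (Protocol 9.8.1.1, SAP 4.7.2.1). The only nominal length is the 28-day cycle in the comparison Pearl formula of SAP 4.7.3.4.

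**The concern.** A cumulative rate has meaning only with its time point. If 16.5% is reached at day 183 and the curve is read later, the true rate at the reading is higher and lies closer to 21%. The whole distance between planning value and limit is 21 − 16.5 = 4.5 points, so each tenth of a point matters. Seven cycles take 183 days only if the mean cycle is 183/7 = 26.1 days. With a longer mean, the stated 90% belongs to an easier question than the one tested. This would be so even if every cycle of every woman were evaluable. At stake is the planning statement, not the validity of the primary analysis.

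**Working it through.** **Inputs** (SAP 4.11.1 unless stated): 1349 enrolled; 26.5% not qualifying for the primary population; 16.5% pregnant in the first six months, exponential; dropout 10% in month 1 and 38% in months 2–6; one-sided 0.025. Decision rule (SAP 4.7.2): Kaplan-Meier estimate + 1.96 × Greenwood SE ≤ 21%.

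**Set-up**
- Women analysed: 1349 × (1 − 0.265) = 991.5.
- Pregnancy hazard: λ = −ln(0.835)/183 = 0.000985 per day.
- Rate at day T: F(T) = 1 − 0.835^(T/183).
- Dropout, taking a month as 30.5 days: −ln(0.90)/30.5 = 0.00345 per day in month 1. After that it is −ln(0.62)/152.5 = 0.00313 if the 38% is conditional on surviving month 1, or −ln(0.52/0.90)/152.5 = 0.00360 if it adds to the 10%. The later hazard is continued past day 183.
- Expected Greenwood SE: (1 − F(T)) × √[(1/991.5) ∫₀ᵀ λ exp(λt + C(t)) dt], where C(t) is the cumulative dropout hazard.
- Power: Φ[(0.21 − F(T))/SE − 1.96].

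**The plan's own figure, at 183 days.** F = 16.5%. With conditional dropout SE = 0.01382, and (0.21 − 0.165)/0.01382 − 1.96 = 1.30, so power is 90.3%. With additive dropout SE = 0.01406 and power is 89.3%. The enrolment needed for 90% is 1337 or 1384, within 3% of 1349. Simulation gives about 87–90%. The stated 90% is therefore reproduced, and it is reproduced with the curve read at day 183.

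**A second sign that planning stopped at month six.** 991.5 × (1 − 0.10 − 0.38) = 515.6, which matches the stated 515 completers. That uses dropout to month six only, although Protocol 6.4 defines completion by seven cycles.

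**The same hazard read at seven cycles.** For a 28-day mean, T = 7 × 28 = 196 and F = 1 − 0.835^(196/183) = 17.56%. With conditional dropout SE = 0.01434, and (0.21 − 0.1756)/0.01434 − 1.96 = 0.44, so power is 66.9%. With additive dropout SE = 0.01461 and power is 65.2%.

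| Assumed mean cycle | Seven cycles | Rate | Distance to 21% | Approximate power |
|---|---|---|---|---|
| 25 days | 175 d | 15.8% | 5.2 points | 96–97% |
| 26 days | 182 d | 16.4% | 4.6 points | 90–91% |
| 27 days | 189 d | 17.0% | 4.0 points | 79–81% |
| 28 days | 196 d | 17.6% | 3.4 points | 64–67% |
| 29 days | 203 d | 18.1% | 2.9 points | 49–52% |

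Simulated values under either reading of dropout fall within about one point of these ranges. Evaluable cycles of 21 to 35 days allow 7 × 21 = 147 to 7 × 35 = 245 days in all.

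**The other reading.** If 16.5% is placed at day 196, with the same dropout hazards, power is about 86–90%.

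**The case against.** The strongest reply is that 16.5% may have been meant as the seven-cycle rate. One line in both documents gives the percentage with no time point, and the endpoint is a seven-cycle percentage, so six months could be a loose name for seven cycles. On that reading almost all the loss disappears and only the wording needs repair. This stands as a possibility. It cannot be taken as settled, because the hazard line and the 183-day sentence both name six months.

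The second reply is that 28 days is not the plan's assumption for this endpoint. That also stands. The 28-day figure belongs to a comparison Pearl formula. At a mean of about 26 days there is no shortfall, and at the 147-day extreme the rate is 13.5% and success is nearly certain. Cycle 0 counts once it lasts at least 21 days from enrolment, so some women's first counted cycle is partial and their seven cycles are somewhat shorter. This effect is small and does not close the gap at a 28-day mean.

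Third, the hazard is specified for the first six months only, so any later value is an extrapolation. At a 28-day mean this is 13 days of a model that the plan itself takes as exponential, and the documents state no lower late hazard.

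A reader might also carry the hazard to the follow-up limit of 245 days and conclude that the planning rate itself exceeds 21%. The documents do not support that. The limit is a censoring cap (252 days in SAP 4.7.2.1), reached only if every cycle lasts 35 days. It is not a planning horizon, and the extrapolation would be about two months.

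**Conclusion.** The mismatch is real: the power statement names seven cycles, and the simulation and hazard name 183 days, with nothing to convert one to the other. Its size is conditional. On the plan's hazard, power stays near 90% at a 26-day mean cycle, is about 80% at 27 days and about two thirds at 28 days. It stays close to 90% at 28 days if 16.5% was meant at seven cycles.

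A reader might infer that the trial's true power is 66%, or that it enrolled too few women. Neither follows, because the time point of 16.5% and the mean cycle length are both left open. The powers above are also illustrative. They count all follow-up time, about 4.5 28-day cycles per woman to day 183, and do not apply the plan's assumption of 3.17 evaluable cycles. That is a separate matter.

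Nor is this an arithmetic slip, since the 90% follows from the plan's inputs at 183 days. The estimator, the 21% limit and the decision rule are unaffected. The point should be corrected because the stated power is relied on and the repair is cheap.

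**What to change.** In Protocol 9.2 and SAP 4.11.1, state the time point to which 16.5% refers and the mean cycle length assumed for seven cycles. Then:

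- If 16.5% is the six-month rate, restate the planning alternative as the seven-cycle rate that the hazard implies (for example 17.6% at a 28-day mean), and give the matching power for 1349 women.
- If 16.5% is the seven-cycle rate, replace the six-month (183 d) wording and rerun the simulation on the seven-cycle horizon.

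The cost is a rerun of an existing simulation and possibly a less favourable stated power. No women are added, and the primary test and its limit do not change.

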## 5 Appendix

### 5.1 Grading for Vulvar, Vaginal, or Cervical Findings

Parameter	Grade 0 Normal	Grade 1 Mild	Grade 2 Moderate	Grade 3 Severe
Epithelial disruption	None	Blisters, ulcerations, superficial disruptions with minimal impact on life – no treatment needed	Blisters, ulcerations, large disruptions – treatment indicated	Severe epithelial disruption with hospitalization indicated
Erythema	None	Erythema covering <50% of surface	Erythema covering ≥50% of surface	Severe erythema with hospitalization indicated
Parameter	Grade 0	Grade 1		
Bleeding	None	Present		
Petechiae	None	Present		
Sloughing	None	Present		

## 6 PROPOSED TABLES, FIGURES AND LISTINGS

### 6.1 Proposed Tables and Figures

Number	Title	Population
14.1.1	Subject Disposition	ITT
14.1.2	Listing of Subjects that Discontinued Prematurely	ITT
14.1.3	Number of Subjects at Each Visit	ITT
14.1.4	Number of Subjects at Each Study Site	ITT
14.1.5	Summary of Protocol Deviations	Safety Population
14.1.6	Demographics	ITT
14.1.6.1	Demographics for the Safety Population	Safety Population
14.1.6.2	Demographics for the Modified Intent-to-Treat Population	MITT
14.1.6.3	Demographics for the Efficacy Evaluable Population	EE
14.1.7	Sensitivity Analysis to Dropouts with Respect to Demography	ITT
14.1.8	Gynecological History	ITT
14.1.9	Contraception Use History	ITT
14.1.10	Obstetric History	ITT
14.1.11	Medical History	ITT
14.1.12	Pre-Treatment Signs and Symptoms	ITT
14.1.13	Incidence of Prior Medications	Safety Population
14.1.14	Incidence of Concomitant Medications	Safety Population
14.1.15	Summary of Compliance as Determined by Contraceptive Method	Safety Population
14.1.16	Percent of Coital Acts as Determined by Contraceptive Method	Safety Population
14.1.17	Percent of Coital Acts with Departures from Study Instructions	Safety Population
14.1.18 (figure)	Percentage of Subjects who Completed the Study or Prematurely Discontinued	ITT

Number	Title	Population
14.2.1	Seven-Cycle Cumulative Pregnancy Probabilities for Subjects with Typical-Use	MITT
14.2.2	Sensitivity Analysis with Respect to the Cycle Length	MITT
14.2.3	Sensitivity Analysis with Respect to the Dosing Time with Respect to Sexual Intercourse	MITT
14.2.4	Seven-Cycle Cumulative Pregnancy Probabilities for Subjects with Perfect-Use	EE
14.2.5	Typical-Use Seven-Cycle Based Pearl Rates	MITT
14.2.6	Perfect-Use Seven-Cycle Based Pearl Rates	EE
14.2.7	Summary of Number of Evaluable Cycles	MITT
14.2.8	Summary of Cycles Excluded from Efficacy Evaluable Analysis	MITT
14.2.9 (figure)	Pregnancy Percentage Curves by Kaplan-Meier Method for Subjects with Typical Use	MITT
14.2.10 (figure)	Pregnancy Percentage Curves by Kaplan-Meier Method for Subjects with Perfect-Use	EE
14.3.1.1	Incidence of Adverse Events	Safety
14.3.1.2	Incidence of Serious Adverse Events	Safety
14.3.1.3	Incidence of Adverse Events Leading to Premature Discontinuation	Safety Population
14.3.1.4	Incidence of Adverse Events by Intensity	Safety
14.3.1.5	Incidence of Adverse Events by Relationship to Treatment	Safety
14.3.1.6	Incidence of Adverse Events by Intensity and Relationship to Treatment	Safety Population
14.3.1.7	Incidence of Adverse Events by Descending Frequency	Safety
14.3.1.8	Sensitivity Analysis to Dropouts with Respect to Adverse Events	Safety
14.3.2.1	Listing of Serious Adverse Events	Safety Population
14.3.2.2	Listing of Adverse Events that Led to Premature Discontinuation	Safety Population
14.3.5.1	Treatment Exposure	Safety Population

Number	Title	Population
14.3.5.2	Incidence of Genitourinary Side Effects by the Time of Symptom Onset after Product Application	Safety Population
14.3.5.3	Incidence of Genitourinary Side Effects by Severity of the Symptom	Safety Population
14.3.5.4	Incidence of Genitourinary Side Effects by Duration of the Symptom	Safety Population
14.3.5.5	Incidence of Genitourinary Infections	Safety Population
14.3.5.6	Dipstick Urinalysis and Urine Culture Results	Safety Population
14.3.5.7	Summary of Wet Mount Assessment Results	Safety Population
14.3.5.8	Change in Gynecological Examination Findings	Safety Population
14.3.5.9	Incidence of Vulvar, Vaginal, or Cervical Findings	Safety Population
14.3.5.10	Sexually Transmitted Infection Test Results	Safety Population
14.3.5.11	Mean Change from Baseline to Final Evaluation for Hematology Analytes	Safety Population
14.3.5.12	Shift from Baseline to Final Evaluation for Hematology Analytes	Safety Population
14.3.5.13	Mean Change from Baseline to Final Evaluation for Clinical Chemistry Analytes	Safety Population
14.3.5.14	Shift from Baseline to Final Evaluation for Clinical Chemistry Analytes	Safety Population
14.3.5.15	Mean Change from Baseline to Each Visit for Vital Signs and Weight	Safety Population
14.3.5.16	Summary of Pregnancy Outcomes	Safety Population
14.3.5.17	Summary of Subject Satisfaction Questionnaires	Safety Population
14.3.5.18	Summary of Sexual Function Questionnaire	Safety Population
14.3.5.19	Summary of Sexual Satisfaction and Lubrication	Safety Population
14.3.5.20	Summary of Pregnancy Intendedness	MITT

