9.10.2 Pregnancy Intendedness

Pregnancy intendedness scale results and change from baseline will be summarized descriptively.

9.11 **Protocol Deviations**

Deviations from the protocol, including violations of inclusion/exclusion criteria, will be assessed in cooperation with the Sponsor and summarized. Subjects whose diaries indicate that they used the assigned study drug incorrectly for every act of intercourse for every menstrual cycle will be excluded from the EE population. Cycles in which the study drug was used incorrectly for one or more coital acts will be removed, and the correct use cycles will be compressed to provide contiguous cycles of correct use.

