### 2.3 Exploratory Objectives

- To assess subject satisfaction (including sexual satisfaction) with Amphora over seven cycles of use
- To assess pregnancy intendedness for subjects treated with Amphora over seven cycles of use
- To assess dosing time deviations for study drug-associated pregnancies

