### 4.3 Analysis Populations

Intent-To-Treat (ITT): all subjects enrolled into the study.

Safety Population: ITT subjects who use at least one application of the study product.

Modified Intent-To-Treat (MITT): Subjects must meet requirements 1, 2, and 3 simultaneously and at least one of 4 or 5 to be included in MITT:

1. between 18 to 35 years of age (inclusive) at enrollment
2. at least one report of pregnancy after being enrolled (subjects with a positive serum pregnancy test at enrollment will not be included in the MITT population).
3. ITT subjects whose diaries indicate they had at least one episode of coitus while using the assigned study product (also referred as "Typical-Use")
4. have at least 1 cycle without any backup contraception or emergency contraception (EC) recorded in the eDiary product use questionnaire
5. became pregnant and the pregnancy had a conception date that occurred after enrollment and within 7 days of the date of last dose of study product.

Efficacy Evaluable (EE): a subset of the MITT population that includes only those subjects whose diaries indicate that they used the study product correctly for every intercourse for at least one menstrual cycle (also referred as "Perfect-Use" or "Per Protocol"). Cycles in which the study product was used incorrectly for one or more coital acts will be removed, and the correct use cycles will be compressed to provide contiguous cycles of correct use.

The Table 2 provides the handling rules of the analysis populations for special situations.

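### The exploratory pregnancy-intendedness table is assigned to MITT, a narrower group than the treated women named in its objective, and no reason is given

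*SAP*

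**What the plan says.** The exploratory objective in SAP 2.3, repeated in Protocol 2.3, is "To assess pregnancy intendedness for subjects treated with Amphora over seven cycles of use".

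The method text names no analysis population. SAP 4.11 says "The pregnancy intendedness scale and its change from the baseline will be summarized descriptively by visit", and Protocol 9.10.2 says "Pregnancy intendedness scale results and change from baseline will be summarized descriptively". The population is therefore set only in SAP 6.1, where Table 14.3.5.20, "Summary of Pregnancy Intendedness", carries the label MITT.

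SAP 4.3 defines the two candidate populations:

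- Safety: "Safety Population: ITT subjects who use at least one application of the study product".
- MITT: "Subjects must meet requirements 1, 2, and 3 simultaneously and at least one of 4 or 5 to be included in MITT". Requirements 1 to 3 are age, a pregnancy report after enrollment, and diary evidence of intercourse while using the product. Requirement 4 is "have at least 1 cycle without any backup contraception or emergency contraception (EC) recorded in the eDiary product use questionnaire". Requirement 5, the alternative to 4, begins "became pregnant and the pregnancy had a conception date that occurred after enrollment and within 7 days of the date of last dose".

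Protocol 9.3 gives MITT the role of primary efficacy population. SAP 4.9 places the satisfaction and sexual-function questionnaires on Safety, and Tables 14.3.5.17 to 14.3.5.19 follow it.

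**The concern.** The table summarises a narrower group than the objective names, and nothing in either document explains why. Membership of the narrower group depends on what happened after enrollment: whether a woman used backup or emergency contraception, whether she conceived, and whether she supplied pregnancy-status and diary data.

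The intendedness item (Protocol Appendix G) asks how a woman would feel if she became pregnant, on a scale from 1 (very unhappy) to 10 (very happy). Use of backup or emergency contraception could plausibly go with that feeling, so the exclusion may not be neutral for the score. At stake is whether the reported distribution describes treated women or only those who qualified for the efficacy analysis.

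**Working it through.** **1. Populations side by side.** MITT requirement 3 needs intercourse with the product, so every MITT woman has used it and is also in Safety. MITT is thus a subset of Safety, and the question is which treated women the table loses. I read SAP requirement 2 in the Protocol 9.3 sense, as a report of pregnancy status.

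| Treated woman | Safety | MITT |
|---|---|---|
| Meets 1-3, at least one cycle free of backup and EC | in | in |
| Meets 1-3, backup or EC in every recorded cycle, conceived on treatment | in | in |
| Meets 1-3, backup or EC in every recorded cycle, no on-treatment conception | in | out |
| No pregnancy status after enrollment | in | out |
| No diary-recorded intercourse with product | in | out |

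The last three rows lose all their scores from the table, baseline included. The third row need not mean long follow-up. The plan assumes dropout of 10% in month 1 and 38% in months 2-6, and a woman who leaves after one or two cycles, each with one backup or EC use, has no free cycle.

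**2. Position in the table list.** Every other table in the 14.3 series of SAP 6.1 is assigned to Safety. Table 14.3.5.20 is the only one assigned to MITT.

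**3. The plan's only figure on exclusions.** SAP 4.11.1 and Protocol 9.2 expect 26.5% of subjects to fall outside the primary efficacy population.

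- Inside: 1349 × (1 − 0.265) = 991.5.
- Cycles: 991.5 × 3.17 = 3143, which reproduces the stated 3143 and confirms that the 26.5% is taken of all enrolled women.
- Outside: 1349 × 0.265 = 357.5, about 357 women for all reasons together.

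Some of these may never have used the product and so are not in Safety either. If u of them were untreated, the share of treated women excluded is (357 − u) / (1349 − u). That is 26.5% at u = 0 and, taking u = 100 as an arbitrary example, 257 / 1249 = 20.6%. So 26.5% is only a loose ceiling. The part due to backup or EC is not given.

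**4. Illustrative shift.** Let f be the share of treated women excluded and d the mean score of those retained minus the mean score of those excluded. The Safety mean equals the MITT mean minus f × d, so the MITT mean differs from the Safety mean by f × d. Both inputs are assumptions.

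| f | d = 1 | d = 2 | d = 3 |
|---|---|---|---|
| 2% | 0.02 | 0.04 | 0.06 |
| 5% | 0.05 | 0.10 | 0.15 |
| 10% | 0.10 | 0.20 | 0.30 |

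If the excluded women score higher instead, the sign reverses.

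**The case against.** MITT is defensible. Its members are all treated women, so the objective's wording does not strictly contradict it. The typical-use pregnancy rate is estimated in MITT, and intendedness in the same women would be natural context for that rate. The Safety rule in SAP 4.9 covers only that section, and intendedness sits apart in 4.11, so the label may be deliberate. The group with backup or EC in every cycle is probably small: inclusion criterion 8 asks for willingness to rely on the study drug alone, with EC as the exception, and Protocol 6.4 has two consecutive backup cycles discussed with the sponsor. Listing 16.4.1 shows intendedness for all ITT women, and Listing 16.2.3.1 shows who was excluded from MITT.

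Much of this stands. It does not supply the missing reason, however, and a listing is not a summary. The context argument is met by a supporting MITT column.

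A reader might infer more: that MITT removes the women most averse to pregnancy and so pushes the mean upward. The documents do not support that direction. Protocol 5.2 offers EC when a woman believes the product was not used properly or feels at risk for another reason, so its use may reflect a single product-use event. Nothing links backup use to scores, and nothing suggests that women missing pregnancy status or diary intercourse score lower. Nor does keeping on-treatment conceivers bias the table relative to Safety, since treated conceivers are in Safety too.

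**Conclusion.** The mismatch holds: the table's population is narrower than its objective, differs from the other questionnaire tables, and is unexplained. That rests on the documents alone. That the exclusion is related to the score is plausible but not shown.

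The illustrative size, 0.02 to 0.30 points, rests on two assumed inputs (2% to 10% of treated women excluded, scoring 1 to 3 points lower). A reader might multiply the planned 26.5% by a 3-point gap and conclude that the mean is overstated by about 0.8 (0.265 × 3 = 0.795). That is not supported. The 26.5% counts enrolled women and all reasons, while the proposed mechanism concerns only backup and EC users. The 3-point gap is an assumed extreme, and one hard to reach if scores are already low because women wanting pregnancy are ineligible (exclusion criterion 5).

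This is a free improvement. The endpoint is exploratory and descriptive, no test or success criterion uses the table, and the primary result, sample size and power are untouched.

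**What to change.** In SAP 6.1, change the population of Table 14.3.5.20 from MITT to Safety. Add one sentence to SAP 4.11 naming the Safety Population, in line with SAP 4.9. Keep an MITT column in the same table as supporting context for the typical-use rate, and state that purpose. Showing the two columns together would also reveal any difference between the populations, so no assumption about direction is needed.

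The cost is one label, one sentence and one extra column. No new data are needed, since the scores are already collected at enrollment and at Visits 3 to 5.
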